Funding Source (if any)	Pending funding from National Institute on Aging

2. Objectives

To make a program that appears to enhance caregiving mastery even more accessible and available to a growing number of dementia family caregivers, we seek to pursue two aims:

Aim 1. Develop a fully asynchronous online Savvy program that incorporates learning activities that promote both knowledge and skill acquisition and develop/enhance caregivers' felt-sense of caregiving mastery.

With input from clinicians, educators, Tele-Savvy facilitators, and caregiver advisors, and assisted by the Roybal Center's Design Studio, we will iteratively develop a storyboard and scripted curriculum for this online educational program. Then, in collaboration with our educational design consultant, we will modify/produce the text and video assets and place them on a continuing education platform that promotes active learning.

Aim 2. Establish the feasibility, acceptability and preliminary efficacy of the online program.

We will use a number of highly reliable channels to recruit 60 family caregivers to take part in a no-control trial of the program, gathering data – at baseline, immediately upon course completion and at 3 months post-baseline – on caregiver distress measures (depression, strain, burden, anxiety), caregiver competence/ mastery, and care recipient quality of life. We will administer investigator-developed evaluation surveys to assess feasibility and acceptability and ad lib improvement comments. We will also seek formative evaluation input through at least 15 semi-structured debriefing interviews, post completion.

3. Background

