The Aim 1 portion of this pilot will recruit approximately 20 individuals to take part in Design Studio activities aimed at developing the a Fully Asynchronous Online Savvy program. With advisory input from clinicians, educators, Tele-Savvy facilitators, and caregivers, and assisted by the Roybal Center's Design Studio, we will iteratively develop a storyboard and scripted curriculum for this online educational program. Aim 1 advisor inclusion criteria: master's/doctoral prepared, hold a professional license, or an informal caregiver; currently or formerly worked with or cared for individuals diagnosed with dementia; and have access to a computer or mobile device with internet. In Aim 2, we will be engaging in the Stage 1B of the NIH Stage Model. The clinical trial portion of this pilot (Aim 2; Stage 1b) will recruit 60 individuals to take part in a test of the Fully Asynchronous Online Savvy program. Aim 2 participant inclusion criteria: primary unpaid caregiver for a community-dwelling PWD; provide at least 10 hours of direct care per week; able to read and understand English; be able to access the course online; naïve to Savvy or Tele-Savvy. Participants will be asked to take part, individually, in a 43-day fully online self-guided learning course that uses instructional and psychoeducational methods to promote and enhance dementia caregiving mastery.

Sources of Materials

All Design Studio research materials will be gathered through audio-recorded participation in 3 group brainstorming activity aimed at developing the online caregiver mastery course. Design Studio data will include input from clinicians, educators, Tele-Savvy facilitators, and caregiver advisors' reflections on the mastery-development needs of dementia family caregivers and on the structure, content, and mode of delivery of the course proposed to address these needs.

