All Aim 2 research materials will be gathered by a trained interviewer through distance means (by phone or videoconference). The data will be in the form of an interview consisting, principally, of well-established instruments focused on the participant's experience of caregiving and his/her observations about and reactions to the care recipient's behavior and well-being. Interviews will be collected at baseline, 2 months, and 3 months. The data for the study will be entered into a secured database using an electronic data capture program such Research Electronic Data Capture (REDCap). The database will be stored on a secure password-protected server and not on individual desktop computers. The code sheet will be password protected and the password will be updated annually. A semi-structured interview will be conducted with a subsample of Aim 2 participants. These interviews will focus on caregivers' experiences of providing care during the pandemic and on their experience of the course developed by this project.

7. Data and Specimen Banking

The proposed Aim 2 research will include data from a community-based sample of 60 informal caregivers of persons living with Alzheimer's disease or a similar neurocognitive illness. In addition to base demographics, the dataset will include four common measures of caregiver depression, anxiety, burden, and mastery. The final dataset also will include additional self-report

measures based on current literature on caregivers. The final dataset will be stored in the Roybal Center data repository. Data from this pilot study will be available to qualified researchers through a data sharing agreement that is fully consistent with NIH data sharing policies and applicable laws and regulations as well as official policies and practices established by the Roybal Center at Emory. Although these data will be de-identified prior to release for sharing, there remains a possibility of deductive disclosure of participants with unusual characteristics. Therefore, this data sharing agreement will require: 1) a commitment only to use the data for research purposes and not to identify any individual participant; 2) a commitment to securing the data using appropriate computer technology; and 3) a commitment to destroy or return the data after analyses are completed.

8. Sharing of Results with Participants

Study results will not be shared with participants or others (e.g., the subject's primary care physicians).

9. Study Timelines

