We anticipate participants will be withdrawn from the study without consent when they do not respond to scheduling baseline and at least 1 follow up interview. When participants self-select to withdraw from the study, one of the PIs will follow up with the participant and confirm withdrawal. Participants can withdraw from the study at any time with no consequence. The team will then discuss if partial data can be included in analysis.

15. Risks to Participants

Protection against risks from participation in Design Studio activities. Participants in the sessions will be identified only by first names, and transcripts of the audio-recorded Design Studio sessions will be fully anonymized, so the threat to confidentiality will be virtually eliminated.

Risks from Research Interviews. There is virtual no risk to the confidentiality of the research data. All study subjects will be assigned ID numbers. The file linking the ID numbers to subjects' identities will be kept in a separate locked filing cabinet in MPI [name]' locked office. There is a minimal risk that participants might find that some elements of the research questionnaires provoke transient emotional responses. The research interviewer will be trained to be alert for such moments and will be able to provide reassurance, offer a break from the interview, and/or reschedule the remaining portion of the interview. In addition, a protocol from another study will be in place to identify participants whose scores on a set of three questionnaires exceed established limits; in such cases, one of the MPIs will contact the individual to check on his/her safety and well-being.

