Risks from Participating in the Asynchronous Online Course. The course will engage participants in a series of self-guided reflections on the condition of the person for whom they are providing care, and it will present material that makes it clear that dementing illnesses are, by their nature, progressive and irreversible. Such reflection and information might cause transient emotional distress for the participant. The course will be framed in a manner that alerts participants to this risk. It will also contain content and exercises meant to assist participants to acknowledge and deal with these and other feelings of distress they might experience in their caregiving. As part of the course, participants will be asked to complete a variety of exercises before they can move to next segments of the course; among these will be exercises asking participants to gauge their own well-being and identify any troubling thoughts they might be experiencing. We will be monitoring these exercises, and if we observe any responses that suggest the possibility that an individual is considering harm to him/herself or to the care recipient, we will contact the person to discuss the situation and provide advice about help-seeking.

The participants to be recruited for this study are dementia caregivers. As such, the target sample, in itself, is not considered among vulnerable populations although we are sensitive to the fact that they may be highly distressed. It is possible that the participants may be pregnant women. We will not exclude women due to pregnancy, however, since their participation in the study is voluntary, they are able to withdraw at any time.

16. Potential Benefits to Participants

We will not assert to participants that taking part in the course will be beneficial to their caregiving, although we are hopeful it will. We will acknowledge that their participation may contribute eventually to the well-being of other caregivers, and this may prove rewarding for them.

17. Data Analysis, Management and Confidentiality

All data entry screens are set up in Research Electronic Data Capture (REDCap) and, where possible, include data delimiters (i.e., skip patterns, valid range limits) to ensure correctness and minimize missing data. Data will be exported into SPSS monthly and syntax run for cleaning, further data verification and file concatenation. Descriptive statistics will be computed through SPSS v 24 to examine participant characteristics. In

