preliminary analyses, descriptive statistics and frequency distributions will be examined to identify outliers and ensure integrity of merged files. Analysis of variance (ANOVA) with repeated measures, non-parametric Kruskal-Wallis ANOVA, and Chi-Square tests will be used to assess preliminary efficacy and establish effect size for a larger study. Internal consistency will be examined using Cronbach's alpha and associated statistics (e.g., item-total correlations, alpha if item deleted). Formal test-retest/inter-rater reliability coefficients will be computed as data are concatenated. NVivo will be used to analyze qualitative data such as focus groups for Aim 1 and interviews for Aim 2. All audio recordings will be transcribed verbatim. The databases will be stored on a secure password-protected server and not on individual desktop computers. The code sheet will be password protected and the password will be updated annually.

The study team for this study will be comprised of the Principal Investigators (Drs. [name] and [name]), and Co-Investigator ([name]). The MPIs will be responsible for the day to day operations of the study including recruitment and data collection management and analysis. The administrative site will be at Emory University, Nell Hodgson Woodruff School of Nursing. All team members have completed CITI training. Study-specific training for staff who will be obtaining data by interview.

[name] is the primary individual charged with identification and reporting of all adverse events (AE) and serious adverse events (SAE). [name] will provide systematic routine monitoring for the following central elements: protocol eligibility (direct source documentation of eligibility as defined in the protocol), appropriateness of consent documentation, and timeliness and accuracy of data. Monitoring reports will be conducted on a bi-weekly basis and as needed, and will be reviewed at the weekly core team meeting of the investigator team.

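### Protocol Sections 2 and 6 anchor the second Aim 2 assessment differently (course completion versus 2 months), with no window and no statement of which governs

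*Combined protocol and SAP*

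**What the plan says.** - **Section 2 (Objectives, Aim 2)** collects outcome data from 60 caregivers, without a control group, at baseline, "immediately upon course completion and at 3 months post-baseline".
- **Section 6 (Procedures Involved)** states: "Interviews will be collected at baseline, 2 months, and 3 months". It names no anchor for the 2 and 3 months; baseline is the natural reading.
- **Section 6** also describes the intervention as a "43-day fully online self-guided learning course". Section 15 (Risks to Participants) adds that "participants will be asked to complete a variety of exercises before they can move to next segments of the course".
- **Section 14 (Withdrawal of Participants)** expects caregivers to be withdrawn "when they do not respond to scheduling baseline and at least 1 follow up interview". After two further sentences, on caregivers who choose to withdraw, it says: "The team will then discuss if partial data can be included in analysis".
- **Section 17 (Data Analysis)** lists "Analysis of variance (ANOVA) with repeated measures" among methods that "will be used to assess preliminary efficacy and establish effect size for a larger study".

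The protocol gives no visit window, no definition of course completion, no course start date relative to baseline, and no rule for the second assessment of a caregiver who does not finish.

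**The concern.** The second assessment is tied to an event in one section and to a calendar date in another. Both statements are current text, and the analysis uses that time point. Two things are at stake.

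The first is what the second time point measures. It is either the state at the end of the course or the state some weeks later, and the spacing to the last interview changes with it.

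The second is who contributes to it. Caregivers move through the course at their own pace and must complete exercises to advance, so finish dates can vary and some may not finish. If the assessment waits for each caregiver's own finish, those who do not finish have none. A repeated-measures ANOVA in its standard form uses only caregivers with all three occasions, so it would lose them altogether, including their 3-month data. The effect size carried to a larger study could then describe mainly those who finish or respond rather than all who enrolled.

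**Working it through.** **Step 1: dates.** The protocol gives the course length (43 days) and the nominal times (2 and 3 months). It does not give the course start, so I assume it is baseline. A month is taken as 28 to 31 days, using one definition throughout each line.

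| Quantity | Formula | Result |
|---|---|---|
| 2 months | 2 × 28 to 2 × 31 | day 56 to 62 |
| 3 months | 3 × 28 to 3 × 31 | day 84 to 93 |
| Gap between the two anchors | 56 − 43 to 62 − 43 | 13 to 19 days |
| Second to third assessment, Section 2 | 84 − 43 to 93 − 43 | 41 to 50 days |
| Second to third assessment, Section 6 | 84 − 56 to 93 − 62 | 28 to 31 days |

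With an assumed 14-day lag from baseline to course start, the scheduled end is day 57. The gap becomes 56 − 57 = −1 to 62 − 57 = 5 days, so it nearly closes.

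**Step 2: who is due a second assessment.**

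| Reading | Non-finisher has a second assessment? |
|---|---|
| Section 2, completion = the caregiver's own finish | No |
| Section 2, completion = scheduled day 43 | Yes |
| Section 6 governs | Yes, at 2 months |

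The 3-month interview stands under every reading.

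**Step 3: illustration of the bias under the first reading.** The documents give no completion rate and no effect, so all inputs here are assumed: 20% non-finishers (12 of 60), effect 0.40 SD in finishers, 0 in non-finishers.

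- Effect in all enrolled: 0.80 × 0.40 + 0.20 × 0 = 0.32 SD.
- Complete-case effect (the 48 finishers): 0.40 SD.
- Difference: 0.40 − 0.32 = 0.08 SD.

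The difference is zero if everyone finishes, if non-finishers benefit equally, or if every caregiver is interviewed.

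**Step 4: set against the pilot's precision.** The standard error of a mean pre-post change with SD 1 and correlation r (assumed 0.5 to 0.7) is √(2(1 − r)/n). With n = 60:

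- r = 0.5: √(1.0/60) = 0.13.
- r = 0.7: √(0.6/60) = 0.10.

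The illustrated bias of 0.08 is below one standard error.

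**Step 5: would a mixed model alone be enough?** Keep the Step 3 assumptions, with the same effects at both follow-ups and equal correlation r between occasions. Non-finishers contribute baseline and 3 months. The model in effect predicts their missing second value from those two, each with weight r/(1 + r).

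- r = 0.5: predicted 0.40 − 0.333 × 0.40 = 0.267; overall 0.80 × 0.40 + 0.20 × 0.267 = 0.37.
- r = 0.7: predicted 0.40 − 0.412 × 0.40 = 0.235; overall 0.80 × 0.40 + 0.20 × 0.235 = 0.37.

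The 3-month estimate is 0.32, as it should be. The second-assessment estimate moves only from 0.40 to 0.37. The anchor therefore matters as well as the model.

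**The case against.** The strongest reply is that the loss of non-finishers depends on one reading. Section 2 speaks of all 60 caregivers. The course has a fixed nominal length, so its completion can mean the scheduled end. Section 6 is the operational section and sets a calendar interview. The summary table in Section 1 gives every Aim 2 participant 3 months, and Section 13 pays per interview. All of this stands. A reader might infer that the schedule builds in the exclusion of non-finishers; the documents do not support that, because two of the three readings avoid it.

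A reader might also infer a large inflation of the effect size. With 40% non-finishers and no benefit in them, the Step 3 formula gives 0.60 × 0.40 = 0.24 against 0.40. Nothing in the documents supports such a rate. The only evidence, in Section 3, is high adherence to the video lessons of the parent program. That program had facilitator-led groups, so the evidence may not carry over, but it does not point to heavy non-completion.

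It is also fair to say that an uncontrolled pre-post change is already a weak basis for sizing a controlled study, and that a team could apply either schedule uniformly. Finally, the Section 14 sentence on partial data follows the sentences on self-withdrawal, so it should not be read as a general rule for missed interviews.

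What the objection does not remove is the conflict itself: two anchors, no window, and nothing that reconciles them.

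**Conclusion.** The conflict over the second Aim 2 assessment is real. It amounts to about 13 to 19 days if the course starts at baseline, and much less if the course starts about two weeks later. The 3-month assessment is unaffected.

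The consequence for non-finishers is conditional. It follows only if completion means each caregiver's own finish, and it reaches the effect size because the named ANOVA drops anyone with a missed interview. That second step applies to any missed interview, whatever its cause. The size of the bias cannot be known from the documents. The 0.08 SD is an illustration on assumed inputs, smaller than the pilot's standard error and possibly zero. Severity is minor to moderate: the point is worth settling because the correction is cheap and the plan intends to reuse the effect size.

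**What to change.** 1. **One anchor.** Reconcile Sections 2 and 6 to a single calendar time counted from baseline (scheduled course end or 2 months, the sponsor's choice) with a stated window. Interview every enrolled caregiver then, whether or not the course is finished. Record course start and completion dates.
2. **One analysis change.** In Section 17, replace the complete-case repeated-measures ANOVA with a mixed model for repeated measures that keeps every caregiver with a baseline and at least one follow-up.
3. **Section 14.** Reword the withdrawal sentence to match. As written, it can mean that baseline plus one follow-up is enough to stay in, or that one missed follow-up leads to withdrawal.

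**Cost.** Protocol wording and one model; the number of planned interviews does not change. Choosing 2 months gives up the measure taken directly after the course and leaves about a month to the last interview. Under either anchor some caregivers may still be mid-course, and some may still be missed.

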Three key preliminary findings from the online Tele-Savvy program drive and support this pilot project. The first finding is that Tele-Savvy seems to have worked. It appears to have demonstrated efficacy in reducing the distress associated with dementia family caregiving and to have increased caregivers' sense of mastery in carrying out the caregiving role. Preliminary results from the first 220 participants in the baseline to six month segment of this three arm trial (Tele-Savvy; Healthy Living attention control; and Usual Care) indicate that Tele-Savvy participants demonstrated statistically significant group-by-time reductions in depression and caregiver strain and statistically significant group-by-time increases in caregiver mastery, compared to those in the other two groups. The second finding is that participants were highly adherent to the asynchronous portion of Tele-Savvy (36 8-15 minute daily video lessons that are viewed whenever and as often as participants wish); they spent, on average, more than 8 hours watching the videos over the 43-day course of the program. The third finding is that the group nature of the synchronous portion of the program constitutes a barrier for participation and a threat to scalability. A substantial number of individuals who consented to be a part of the trial of the program were never able to participate because their schedules precluded incorporating them into online groups.

4. Study Endpoints

Primary endpoints that will be measured are depression (CES-D), burden (Zarit), anxiety (STAI), mastery (Pearlin), and care recipient behavior (RMBPC).

5. Study Intervention / Design

The proposed intervention for this study is a Fully Asynchronous Online Savvy program. This proposed research follows the NIH Stage model for intervention development. In Aim

1, we will be engaging in Stage 1A of the model. In Aim 2, we will be engaging in the Stage 1B of the NIH Stage Model.

6. Procedures Involved

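### Repeated-measures ANOVA in its standard form uses only caregivers with all three interviews, and the plan gives no other missing-data method for the effect size it passes to a larger study

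*Combined protocol and SAP*

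**What the plan says.** Aim 2 is uncontrolled. Section 2 states: "We will use a number of highly reliable channels to recruit 60 family caregivers to take part in a no-control trial of the program". Section 6 sets three assessments: "Interviews will be collected at baseline, 2 months, and 3 months". Section 4 lists five primary endpoints: CES-D, Zarit, STAI, Pearlin mastery and RMBPC.

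Section 17 gives the efficacy analysis in one sentence: "Analysis of variance (ANOVA) with repeated measures, non-parametric Kruskal-Wallis ANOVA, and Chi-Square tests will be used to assess preliminary efficacy and establish effect size", the effect size being for a larger study. It does not say which of the three methods supplies that effect size. It names no analysis set, mixed model, imputation or sensitivity analysis. Its only remark on missing data concerns data-entry controls. Section 18 lists data completeness and retention as items for monitoring reports, which is not an analysis rule.

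Section 14 expects some caregivers to be "withdrawn from the study without consent when they do not respond to scheduling baseline and at least 1 follow up interview". It then turns to caregivers who withdraw themselves, and closes: "The team will then discuss if partial data can be included in analysis".

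**The concern.** There are two separate points, and the first carries the weight.

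**The efficacy analysis.** Standard repeated-measures ANOVA needs a value at every time. A caregiver with a baseline and one follow-up would contribute nothing, so interviews already collected would go unused. If the reason for loss is related to the scores, the mean change among completers differs from the mean change in everyone who started. Because that figure is meant to plan a larger study, an error in it carries forward.

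**Partial data after withdrawal.** Section 14 gives no criterion or timing. It also leaves unclear whether the discussion covers caregivers withdrawn by the team as well as those who leave by choice. Inclusion could therefore be settled after scores are known.

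**Working it through.** **The plan's own figures.** Section 23 gives 12 caregivers per month for 5 months: 12 × 5 = 60. With Aim 1, 20 + 60 = 80, as in Section 12. Both reproduce. The documents give no dropout rate, SD, correlation or target effect, so everything below is assumed.

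**Counts.** Let m be the loss at each follow-up, 10% or 20%.
- Independent misses: all three interviews 60(1−m)² = 48.6 or 38.4; one follow-up only 60·2m(1−m) = 10.8 or 19.2.
- Permanent dropout (m lost at 2 months, then m of those remaining at 3 months): all three 60(1−m)² = 48.6 or 38.4; one follow-up only 60·m(1−m) = 5.4 or 9.6.
- Full overlap: all three 60(1−m) = 54 or 48; one follow-up only 0.

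**Precision, if loss is random.** Assume unit variances and equal correlation r of 0.5 to 0.7 between interviews, with large-sample formulas. Let p be the proportion with all three interviews and q the proportion with a 2-month interview. For the mean change from baseline, 60 × variance is:
- complete-case: 2(1−r)/p;
- mixed model at 2 months, dropout or full overlap: (1−r²)/q + (1−r)²;
- mixed model at 3 months, dropout: (1−2r²/(1+r))/p + (r/(1+r))²(1−r²)/q + (1−r)².

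Example, dropout with m = 10% and r = 0.5 (q = 0.90, p = 0.81):
- complete-case: 1/0.81 = 1.235;
- model at 2 months: 0.75/0.90 + 0.25 = 1.083, ratio √(1.083/1.235) = 0.937;
- model at 3 months: 0.823 + 0.093 + 0.25 = 1.166, ratio √(1.166/1.235) = 0.972.

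Independent misses have no such short form. Those ratios come from inverting the summed normal information over the missingness patterns.

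| Pattern | SE ratio, m = 10% | SE ratio, m = 20% |
|---|---|---|
| Independent, either visit | 0.933–0.935 | 0.866–0.870 |
| Dropout, 2 months | 0.937–0.942 | 0.872–0.881 |
| Dropout, 3 months | 0.972–0.978 | 0.945–0.958 |
| Full overlap, either visit | 0.987–0.992 | 0.975–0.985 |

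The standard error is thus smaller by 7–13%, by 6–13% at 2 months and 2–6% at 3 months, and by 1–3%, respectively.

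**Bias, if loss is selective.** Assume a true change of −0.30 SD (lower is better) at both visits, and loss of 35% in the worse half and 5% in the better half of whatever drives it, so 20% overall. The simulation used 2 million caregivers per correlation. Ranges run from r = 0.5 to r = 0.7.

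| Loss driven by | Complete-case, 2 mo | Complete-case, 3 mo | Model, 3 mo, only month 3 lost | Model, both lost, 2 mo | Model, both lost, 3 mo |
|---|---|---|---|---|---|
| Baseline | −0.226 to −0.255 | −0.226 to −0.255 | −0.30 | −0.30 | −0.30 |
| 2-month score | −0.375 to −0.345 | −0.30 | −0.30 | −0.413 to −0.377 | −0.339 to −0.333 |
| 2-month change | −0.451 to −0.416 | −0.376 to −0.358 | −0.30 | −0.414 to −0.399 | −0.339 to −0.341 |
| 3-month score, unseen | not used | −0.376 to −0.345 | −0.401 to −0.365 | not used | not used |
| 3-month change, unseen | not used | −0.450 to −0.416 | −0.401 to −0.383 | not used | not used |

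The largest complete-case error is 0.451 − 0.30 = 0.15 SD. The 95% half-width for mean change at n = 60 is t(59)·√(2(1−r)/60) = 0.258, 0.231 and 0.200 for r = 0.5, 0.6 and 0.7.

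**Partial data.** A strict complete-case ANOVA excludes any caregiver missing an interview, whatever the team decides, so the Section 14 discussion cannot alter it. For an analysis that can use incomplete data, the question is whether those deciding could know scores. Section 17 says "The MPIs will be responsible for the day to day operations of the study including recruitment and data collection management and analysis" and "Data will be exported into SPSS monthly". Section 15 has an MPI contact caregivers whose questionnaire scores exceed set limits. Knowledge of scores is therefore possible.

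**The case against.** The strongest reply is that a reader might infer from Section 17 that the protocol commits to complete-case analysis. It does not. That is a property of the named method in standard form, and Section 14 at least contemplates using partial data. This stands: the plan leaves the handling of missing interviews unstated.

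A reader might also take 11–19 lost caregivers as the expected size. That needs independent misses at interviews one month apart. Permanent dropout is at least as plausible and gives 5–10. The plan also works to limit loss, through a gift card per interview, remote collection, and interviews that can be split or rescheduled. Every complete-case count above (38 to 54) exceeds the minimum of 30 cited for the sample size. All of this stands.

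A third inference would be that the team will choose partial data to suit the result. The documents do not support it. Monthly exports are for cleaning and verification, and knowledge of scores is hard to avoid in an open single-arm pilot. What remains is a missing rule.

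The mixed model is not uniformly better. When both follow-ups are lost because of the 2-month score, or month 3 is lost because of the unseen 3-month score, it is further off than complete-case. This argues for reporting both results, not for leaving the method unstated.

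Lastly, uncontrolled change cannot separate programme effect from time or regression to the mean under any missing-data method. That lowers the stakes, but the effect size is still a stated product of the pilot.

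**Conclusion.** The point holds as a gap in specification with a cheap improvement available. As named, the ANOVA would set aside collected interviews whenever a caregiver has only one follow-up, and nothing in the documents overrides this.

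The precision at stake ranges from negligible (full overlap) to modest (independent misses). Bias could run either way: loss driven by baseline distress understates improvement, while loss driven by poor follow-up scores can overstate it. A claim that the effect size will be inflated is not supported. In the assumed scenarios the bias stays below the sampling uncertainty at n = 60. All of these sizes rest on assumed loss rates, correlations and true change.

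The Section 14 point is secondary and becomes live only with a method that can use partial data. Overall severity is minor to moderate for a single-arm feasibility pilot.

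**What to change.** **Section 17.** For each of the five Section 4 endpoints, replace repeated-measures ANOVA with a linear mixed model (categorical time, unstructured covariance) using every available interview from every caregiver with a baseline. State that this model supplies the effect size. Report the complete-case result beside it, with one missing-not-at-random sensitivity analysis, for example assuming no improvement in caregivers with a missing follow-up. At 20% loss that example equals 0.8 × the complete-case change. With baseline-driven loss it gives −0.18 to −0.20 against a true −0.30, so it should be read as a bound.

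**Section 14.** As a consequence, replace the discussion sentence with a rule that data collected before withdrawal will be analysed unless the participant asks for removal. Say that it covers both routes of withdrawal, and check it against the consent form.

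**Cost.** Two replaced sentences and two short additions, with no extra participants or visits. The downside is slightly more analysis work and a missing-at-random assumption. When loss depends on unseen scores, the model can be further off than complete-case, which is why the other two results are reported with it.
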